C.2.4. fMRI: MR scanning at WSU will be performed on a 3.0 Tesla Siemens Magnetom Verio System using an industry-leading 32-channel head-coil for superior image quality. We will use a multi-band EPI sequence [similar to: TR = 2000ms; TE = 30ms; Flip = 73°; 128x128 matrix; FOV = 256 mm; 66 slices; 2.0 x 2.0 x 2.0 mm voxels], which we are currently using in PI [name]'s K01 project. A high-resolution structural image will provide precise anatomical localization. Whole-brain fMRI blood oxygen-level dependent (BOLD)-related signal measures will be acquired to measure task- and drug-related effects and to minimize susceptibility artifact (signal loss) at the medial temporal lobe (including the AMYG and the vmPFC)¹³³⁻¹³⁵.

C.2.5. General Statistical Approach: All analyses will use a conventional alpha level of 0.05 and all tests will be two-tailed. To evaluate the main effects, Analysis of Variance will be used for neuroimaging (i.e., BOLD percent signal change (PSC)) and peripheral measures of fear (e.g., SCR, US expectancy, SUDS, psychological/mood measures). We will also include covariates such as gender and childhood trauma/adversity

if found unbalanced and correlated ($r > 0.03$) with the outcome variable (e.g., MANCOVA, ANCOVA). If significant, multivariate analysis will be followed by univariate analysis, which if significant, will be followed-up with simple effects analysis (e.g., independent t-tests, paired t-tests). In addition to omnibus tests, planned comparisons will be used to test specific hypotheses such as THC dose (vs. PBO) on fear extinction in PTSD, as well as comparisons between THC doses; if there is no significant difference between THC doses we will examine potential positive trends with increasing dose. To evaluate relationships, Pearson correlations will be used along with scatterplots to examine the nature of the relationships. Hochberg step-down multiplicity adjustment will be used to control for all multiple comparisons¹³⁶. Confidence intervals and effect sizes will be also be calculated.

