Specific Aim 1 (R61 Primary Target Engagement): Assess effects of THC on recall of extinction learning and vmPFC and/or HPC activation in PTSD patients in a dose-finding study. *Hypothesis 1A: Relative to PBO, THC will dose-dependently increase vmPFC and/or HPC activation to a CS+E (vs. CS+U) during proximal (24 hr post-extinction learning) and/or distal (1 week post-extinction learning) recall of extinction learning in PTSD.* PCS (CS+E vs. CS+U) with ROIs (vmPFC, HPC) will be submitted to MANCOVA with Group (PTSD-5mg, PTSD-10mg, PTSD-PBO, TEC) as between-subjects factor and Recall (24 hr, 1 week) as within-subject factor, controlling for potential confounds. In addition to omnibus tests, planned comparisons will examine dose of THC on prefrontal-limbic engagement during recall of extinction learning in PTSD relative to PBO, and comparisons between THC doses; if there is no significant difference between THC doses we will examine potential positive trends with increasing dose. Similar analyses will be conducted using other variables of interest such as psychological measures, mood state, and drug effects. *Hypothesis 1B: Relative to PBO, THC will dose-dependently decrease peripheral measures of extinction recall (“extinction recall index” (ETI), US expectancy, SUDS) to the CS+E during a proximal and/or a distal test of extinction learning recall in PTSD.* These data will be submitted to MANCOVA with Group (PTSD-5mg, PTSD-10mg, PTSD-PBO, TEC) as between-subjects factor and Recall (24 hr, 1 week) as within-subject factor, controlling for potential confounds. Analyses will be comparable to that used to examine BOLD activation (*Hypothesis 1A*). *Hypothesis 1C: vmPFC and/or HPC activation will correspond with extinction recall success (i.e. higher ETI, lower US expectancy, lower SUDS).* Pearson correlation analyses will be used to correlate measures of BOLD activation (PSC) and peripheral measures (e.g., SCR, ETI, US expectancy) to the CS+E vs. CS+U within and across the two contexts/recall and renewal tests.

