R61 Power Analysis: We have conducted several power calculations in our previously published work used to determine the sample sizes proposed here. First, we have consistently found that an *n* of 14-16 healthy controls and an *n* of 14-16 PTSD patients provide adequate power to observe: 1) SCR differences and AMYG, vmPFC, HPC signal differences between groups during fear extinction and/or extinction recall; and 2) THC's effects on ETI and AMYG, vmPFC, and HPC activation in healthy controls. Similarly, normalization of corticolimbic responsivity to affective stimuli has been observed following exposure-based therapy in an *n* of 14 anxious patients¹⁴⁸ and following administration of a serotonin selective reuptake inhibitor (SSRI) with an *n* of 21 anxious patients¹⁴⁹. Given that the effect sizes tested within- and between-groups in previous fMRI studies have ranged between moderate to large (Cohen *d* = 0.7 - 1.5) with the anticipated cohort of 20 participants per group (PTSD-5mg, PTSD-10mg, PTSD-PBO, TEC), who complete the entire protocol with usable fMRI and SCR data, will confer >80% power to detect an effect size 0.72 or higher after necessary multiplicity adjustment.

PROTECTION OF HUMAN PARTICIPANTS

This Human Participants Research meets the definition of a clinical trial.

1. Risks to Human Participants

a. Human Participants Involvement, Characteristics, and Design

Involvement of Human Participants:

The total time commitment estimated per participant is 8.5-13 hr across all study visits. This is broken down below:

Visit 1: Screening & Study Entry: Approximately 3 hours for participants, unless a participant has already completed any of the screening assessments as part of another separate study. In this case, if the overlapping screening assessments were completed no more than 1 month prior to Visit 1 and the participant has signed HIPPA Authorization allowing us to access this prior data, Visit 1 will be approximately 1.5 hr.

Note: Due to the length and rigor of this initial screening process, it may sometimes be necessary for participants to complete screening measures across more than one visit (e.g., schedule conflicts). All screening measures will be completed within 2 weeks of the consent date.

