Vulnerable Populations

This study will include women of child-bearing potential and college students. However, we will conduct urine pregnancy tests at the screening visit (Visit 1) and at the beginning of Visit 3 to make sure that women are not pregnant. Of note, if the participant is unable to provide a urine sample at Visit 1 (e.g., currently menstruating), we will conduct a urine pregnancy test at the beginning of visit 2. We will also conduct pregnancy tests if the study staff and/or participant have reason to believe they may be pregnant. In addition, participation of college students in this study is completely voluntary, as it is for all participants, and will not be required by any course.

Study Group Assignment

Individuals with PTSD will be randomized to a THC or PBO condition. In our previous studies we have shown that 7.5mg of THC facilitates extinction recall and modulates prefrontal and hippocampal activation in healthy humans volunteers^{55,113}. Moreover, PI [name] has preliminary data to suggest that 7.5mg of THC may facilitate extinction recall in PTSD, but it is not known whether this is the MED. This is an initial step in translation to be tested in the R61 phase. Therefore, we will have a low 5mg condition and a high 10mg condition should 5mg be too low to detect effects. Of note, a 10mg dose of THC does not typically produce anxiety¹⁵¹ or strong negative effects on cognition¹⁵². We aim to identify the MED that facilitates recall of extinction learning. Dronabinol is administered only by the oral route and will be placed in opaque capsules with dextrose filler. Placebo capsules will be identical in appearance but will contain only dextrose. All capsules will be administered to participants in double-blind conditions and participants assigned to receive dronabinol (two-thirds of the PTSD participants) will only receive dronabinol on one occasion.

Study medication, dronabinol or PBO, will be dispensed to participants by PI [name], who possesses a Schedule II-V controlled substance research license through the State of Michigan and the DEA and has experience in the use of dronabinol and PBO in human participant research. A registered pharmacist will handle

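### The conditional dose-trend step is undefined, and on its natural readings it cannot tell a plateau from a dose response, so it should not count as evidence of dose-dependence

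*Combined protocol and SAP*

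**What the plan says.** Hypothesis 1A in C.2.9 predicts that, relative to placebo, "THC will dose-dependently increase vmPFC and/or HPC activation". Study Group Assignment gives the purpose of having two doses: "We aim to identify the MED that facilitates recall of extinction learning".

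C.2.5 plans omnibus tests, then comparisons of THC dose with placebo and of the THC doses with each other. It adds "if there is no significant difference between THC doses we will examine potential positive trends with increasing dose", and C.2.9 repeats this for Aim 1. C.2.5 also says "All analyses will use a conventional alpha level of 0.05 and all tests will be two-tailed" and "Hochberg step-down multiplicity adjustment will be used to control for all multiple comparisons".

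Neither section gives the trend test's scores, the arms that enter it, its alpha or its place in the Hochberg family. No section gives a rule for declaring an MED. The R61 Power Analysis says that 20 per group "will confer >80% power to detect an effect size 0.72 or higher after necessary multiplicity adjustment". It gives no power for 10mg v 5mg or for a trend.

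**The concern.** The trend is examined only after the direct comparison of the two doses has failed. It therefore gives the dose claim a second chance, through a test that can be chosen once the data are in hand. If that test is driven by the difference between 10mg and placebo, a positive result shows that the drug does something. It does not show that more drug does more.

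The study is described as dose-finding. Describing equal effects at 5mg and 10mg as a trend with increasing dose would misstate the dose information that it was run to obtain. The Data and Safety Monitoring Plan also uses a significant advantage of 10mg over 5mg as its example of grounds for a dosing amendment, so the between-dose question has consequences within the trial.

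**Working it through.** **Inputs.** 26 per PTSD arm with about 25% loss (C.2): 26 × 0.75 = 19.5, so about 20 evaluable. Two-sided alpha of 0.05 (C.2.5). Doses 0, 5 and 10mg, equally spaced. Prior effects of d = 0.7 to 1.5 and a design effect of 0.72 (R61 Power Analysis). The documents give no 10mg v 5mg effect and no dose-response shape. The plateau and linear shapes below are assumptions.

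**The plan's own figure.** For 20 v 20 at d = 0.72, the noncentrality is 0.72 × √(20/2) = 2.28 on 38 df. Power is 60% unadjusted, 48% at alpha 0.025 and 42% at 0.0167. The stated >80% is not reproduced for a two-group comparison. A paired comparison with n = 20 reaches 86% unadjusted (78% at 0.025). In any case the statement does not address the difference between doses.

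**What the trend test is.**
- *THC arms only.* With two groups, a trend is the 10mg v 5mg difference, which has just been found non-significant.
- *Placebo as 0, linear scores, equal arms.* The mean score is 5, so the weights are 0 − 5, 5 − 5 and 10 − 5, that is −5, 0 and +5. The test statistic is (mean at 10mg − mean on placebo) / (s√(2/n)), which is the 10mg v placebo comparison.
- *Other scores.* With log(dose + 1) scores, the 5mg weight is +0.16 of the score range. The plateau probabilities below become 67% (d = 0.72) and 84% (d = 0.9). With the Jonckheere-Terpstra test they are 55% and 74%. These do not separate the two shapes either.

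**Power of 10mg v 5mg**, n = 20 per arm, linear response, so the difference is half of the 10mg effect:

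| 10mg v placebo, d | 10mg v 5mg, d | Power |
|---|---|---|
| 0.70 | 0.35 | 19% |
| 0.72 | 0.36 | 20% |
| 0.90 | 0.45 | 28% (29% with the three-arm pooled variance, 57 df) |
| 1.50 | 0.75 | 64% |

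80% power would need 122 per arm at a difference of 0.36, or 78 at 0.45.

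**The sequence** (three-arm simulation, pooled variance, 57 df, linear contrast). Under a plateau, 10mg v 5mg is non-significant in 95% of trials. The linear contrast is significant in 61% at d = 0.72 and 80% at d = 0.9. The products, 0.95 × 0.61 = 0.58 and 0.95 × 0.80 = 0.76, agree closely with the simulated joint probabilities. Under a linear response at d = 0.72, 0.80 of trials have a non-significant dose comparison, and 0.546 of those then show a significant trend: 0.80 × 0.546 = 0.437.

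| 'No dose difference, positive trend' | d = 0.72 | d = 0.9 |
|---|---|---|
| Plateau, unadjusted 0.05 | 58% | 76% |
| Plateau, Hochberg over the three pairwise contrasts | 45% | 66% |
| Truly linear, unadjusted 0.05 | 44% | 53% |

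Like for like (unadjusted), the pattern is more frequent when 10mg adds nothing over 5mg than when the response is linear. It also appears in 56% of trials when the 10mg effect is smaller than the 5mg effect (0.72 v 1.0).

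**The case against.** Several points on the other side stand.

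- The documents name no trend contrast. A reader might infer that the plan adopts a test giving the 5mg arm zero weight. That holds only for linear scores with equal arms, which is the most common choice but is not stated.
- A reader might infer that the MED rests on 10mg v 5mg and the trend. It does not: each dose v placebo is also planned. In the plateau trials that end in a positive trend, 5mg v placebo is itself significant in 76% (d = 0.72) and 87% (d = 0.9), or 63% and 78% after Hochberg. The results would often show an effect at 5mg.
- A reader might infer that a plateau would usually be reported as a dose trend. At d = 0.72 the 58% falls to 45% once the plan's own multiplicity rule is applied. The wording about examining trends also does not commit the authors to a claim of dose-dependence.
- Hypothesis 1A is framed relative to placebo, and a contrast that includes placebo is a legitimate test of a response against none.

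The last point does not rescue the step. A test of response against no response answers a different question from whether 10mg exceeds 5mg, and the plan turns to it precisely when that second question has not been answered. Leaving the test undefined adds freedom of choice and removes none of the difficulty.

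**Conclusion.** The point holds in a limited form. The conditional trend step is undefined, and no natural version of it supports a claim that effect rises from 5mg to 10mg. With 20 per arm, a plateau leads to 'no dose difference, positive trend' in about 58-76% of trials unadjusted, or 45-66% with Hochberg, for d = 0.72-0.9. A truly linear response gives about 44-53% unadjusted. The pattern therefore does not favour a dose response over a plateau.

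The direct 10mg v 5mg test has about 20-29% power under a linear response with a 10mg effect of 0.72-0.9. Over the plan's prior range of 0.7-1.5 it runs from about 19% to 64%, so the low figures are not the whole range. All of these rest on the assumed shapes, equal arms of 20 and a common variance.

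The documents do not support saying that the MED depends on this step. What is missing is a stated rule for reading it.

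**What to change.** Change the wording of C.2.5 and C.2.9, with no change to design or data collection:

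1. Remove the conditional trend step as evidence of dose-dependence. If a trend that includes placebo is kept, define its scores and its place in the Hochberg family, and report it only as evidence of a drug effect against placebo.
2. Base any claim of dose-dependence on the 10mg minus 5mg difference with its confidence interval. C.2.5 already commits to intervals and effect sizes.
3. State that a non-significant difference between doses is inconclusive at this power and is not evidence that the doses are equivalent.
4. State that the MED is read from the planned dose v placebo comparisons under the stated multiplicity adjustment.

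A fixed sequence (high dose v placebo, then low dose v placebo, each at 0.05) is an option and not a required correction. At d = 0.9 it gives 80% power for 10mg v placebo, against 66-69% with Hochberg over three contrasts. Under a plateau it gives no gain for 5mg (45% v 47% at d = 0.72, 69% v 69% at d = 0.9), and it loses if the response is not monotone.

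The cost is that fewer trials of this size will be able to claim dose-dependence.

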Specific Aim 1 (R61 Primary Target Engagement): Assess effects of THC on recall of extinction learning and vmPFC and/or HPC activation in PTSD patients in a dose-finding study. *Hypothesis 1A: Relative to PBO, THC will dose-dependently increase vmPFC and/or HPC activation to a CS+E (vs. CS+U) during proximal (24 hr post-extinction learning) and/or distal (1 week post-extinction learning) recall of extinction learning in PTSD.* PCS (CS+E vs. CS+U) with ROIs (vmPFC, HPC) will be submitted to MANCOVA with Group (PTSD-5mg, PTSD-10mg, PTSD-PBO, TEC) as between-subjects factor and Recall (24 hr, 1 week) as within-subject factor, controlling for potential confounds. In addition to omnibus tests, planned comparisons will examine dose of THC on prefrontal-limbic engagement during recall of extinction learning in PTSD relative to PBO, and comparisons between THC doses; if there is no significant difference between THC doses we will examine potential positive trends with increasing dose. Similar analyses will be conducted using other variables of interest such as psychological measures, mood state, and drug effects. *Hypothesis 1B: Relative to PBO, THC will dose-dependently decrease peripheral measures of extinction recall (“extinction recall index” (ETI), US expectancy, SUDS) to the CS+E during a proximal and/or a distal test of extinction learning recall in PTSD.* These data will be submitted to MANCOVA with Group (PTSD-5mg, PTSD-10mg, PTSD-PBO, TEC) as between-subjects factor and Recall (24 hr, 1 week) as within-subject factor, controlling for potential confounds. Analyses will be comparable to that used to examine BOLD activation (*Hypothesis 1A*). *Hypothesis 1C: vmPFC and/or HPC activation will correspond with extinction recall success (i.e. higher ETI, lower US expectancy, lower SUDS).* Pearson correlation analyses will be used to correlate measures of BOLD activation (PSC) and peripheral measures (e.g., SCR, ETI, US expectancy) to the CS+E vs. CS+U within and across the two contexts/recall and renewal tests.

R61 Power Analysis: We have conducted several power calculations in our previously published work used to determine the sample sizes proposed here. First, we have consistently found that an *n* of 14-16 healthy controls and an *n* of 14-16 PTSD patients provide adequate power to observe: 1) SCR differences and AMYG, vmPFC, HPC signal differences between groups during fear extinction and/or extinction recall; and 2) THC's effects on ETI and AMYG, vmPFC, and HPC activation in healthy controls. Similarly, normalization of corticolimbic responsivity to affective stimuli has been observed following exposure-based therapy in an *n* of 14 anxious patients¹⁴⁸ and following administration of a serotonin selective reuptake inhibitor (SSRI) with an *n* of 21 anxious patients¹⁴⁹. Given that the effect sizes tested within- and between-groups in previous fMRI studies have ranged between moderate to large (Cohen *d* = 0.7 - 1.5) with the anticipated cohort of 20 participants per group (PTSD-5mg, PTSD-10mg, PTSD-PBO, TEC), who complete the entire protocol with usable fMRI and SCR data, will confer >80% power to detect an effect size 0.72 or higher after necessary multiplicity adjustment.

PROTECTION OF HUMAN PARTICIPANTS

This Human Participants Research meets the definition of a clinical trial.

1. Risks to Human Participants

a. Human Participants Involvement, Characteristics, and Design

Involvement of Human Participants:

The total time commitment estimated per participant is 8.5-13 hr across all study visits. This is broken down below:

Visit 1: Screening & Study Entry: Approximately 3 hours for participants, unless a participant has already completed any of the screening assessments as part of another separate study. In this case, if the overlapping screening assessments were completed no more than 1 month prior to Visit 1 and the participant has signed HIPPA Authorization allowing us to access this prior data, Visit 1 will be approximately 1.5 hr.

Note: Due to the length and rigor of this initial screening process, it may sometimes be necessary for participants to complete screening measures across more than one visit (e.g., schedule conflicts). All screening measures will be completed within 2 weeks of the consent date.

Visit 2: Fear Acquisition: Approximately 1 hr for all participants. Participants are considered enrolled in the study once they have begun Visit 2 (if enrolled in PTSD group, participant will be randomized). Visit 2 will occur within 6 months of Visit 1. If more than 6 months have passed, we will re-do Visit 1 before the participant is able to complete visits 2 – 5.

Visit 3: Fear Extinction: Approximately 5 hr for those receiving a capsule (PTSD groups) or approximately 3 hours for those not receiving a capsule (TEC group)

Visit 4: Fear Extinction Recall and Fear Renewal Test (approximately 24 hr after extinction, but no more than 1 week later): Approximately 1.5 hr

Visit 5: Fear Extinction Recall, Fear Renewal Test, & Debriefing (approximately 1 week after extinction, but no more than 3 weeks later): Approximately 1.5 hr

Nature of Participant Population: Participants of both genders will be included in the study and the age range of participants will be from 18-60. Persons below 18 or above 60 are excluded because beyond this range age may influence response to the drugs. Furthermore, the relatively small age range is intended to reduce variation in performance on the behavioral task. There are no enrollment restrictions based upon race or ethnic origin. Candidates will undergo a structured clinical psychiatric interview¹⁵⁰ and complete questionnaires related to their general physical health, current medications, with a detailed section on current and lifetime drug and alcohol use. This study will not involve vulnerable populations.

The number of participants expected to participate is 104: 78 trauma-exposed participants with PTSD and 26 trauma-exposed participants without PTSD (TEC; demographically matched). There will be 3 experimental groups: PTSD participants will be assigned to 5mg of THC (n=26), 10mg of THC (n=26), or a placebo (PBO) (n=26). The 26 TEC participants will not receive THC or PBO. With the conservative anticipation 25% will fail to complete all parts of the study, we estimate 20 PTSD participants in each condition (60 PTSD participants in total) and 20 TEC participants will complete the study for a total of 80 participants. Participants will be recruited from the Detroit community and mental health clinics. We will enroll up to 175 participants to guarantee enough viable data and to account for participant drop out.

Recruitment

Participants will be recruited from several sources including flyers and webpage advertisements on Academica. In addition, we will also recruit patients seeking treatment at the Trauma Recovery Center of Southeast Michigan, Wayne State University (WSU) Physicians Group, North Central Health Center in Detroit, Detroit Wayne Mental Health Authority, St. John Providence Eastwood Clinics, WSU Psychology Clinic, WSU Clinical Research Center

in Detroit. Current staff in the Departments of Psychiatry and Psychology and related clinical departments at WSU will be informed about the study to pass along the information (in flyer format) to their participants. In addition, individuals who participate in the study may earn additional compensation for referring other people to the study. Once a participant contacts the project coordinator/research assistant at WSU, they will explain the study to the participant and schedule the participant to come in for a screening and orientation session (Visit 1) at the Eugene Applebaum College of Pharmacy and Health Science (EACPHS) building.

Retention

Strategies for participant retention will be discussed regularly in weekly research meetings, and will be practiced for optimized retention such as contact with the PI and her research team during the study, phone reminders/confirmation of visits, established contact with the study coordinator, arrangements for transportation (as needed) at each visit, reimbursement for parking/travel at each visit and for time and effort. Also, office hours are flexible (e.g., 7am-7pm during the week with weekend availability). Based on these strategies, we anticipate that drop-out will be minimized to less than 25% of the sample.

Inclusion Criteria

Inclusion criteria across all groups will be: (a) generally medically and neurologically healthy, including no evidence of intellectual disability or serious cognitive impairment that would interfere with task performance; (b) between the ages of 18-60; (c) willing and able to give informed consent; (d) exposure to Criterion A stressor as defined by the CAPS-5 and identified by the LEC-5, regardless of type of trauma (e.g., civilian or combat).

Inclusion criteria for the PTSD group will be: (a) significant PTSD severity as indicated by a clinician-administered PTSD scale for DSM-5 (CAPS-5) diagnosis and/or score (see below) of ≥ 25 of at least the past month prior to study entry (primary PTSD will be identified as the patient's primary concern). *Inclusion criteria for the TEC group will be:* (a) absence of any history of PTSD symptoms (CAPS-5 < 25 and/or no diagnosis), related to any type of trauma.

Exclusion Criteria

Exclusion criteria across groups will be: (a) exclusively left-handed (i.e., score of -100.00 on Handedness Questionnaire); (b) risk of harm to self or others that requires immediate intervention; (c) presence of contraindications, current or past allergic or adverse reaction, or known sensitivity to cannabinoid-like substances (dronabinol/marijuana/cannabis/THC, cannabinoid oil, sesame oil, gelatin, glycerin, and titanium dioxide); (d) lack of fluency in English; (e) currently pregnant (positive pregnancy test or self-report), planning pregnancy, or lactating (women); (f) traumatic brain injury (as defined by The American Congress of Rehabilitation as a person who has had a traumatically induced physiological disruption of brain function (i.e., the head being struck, the head striking an object, and/or the brain undergoing an acceleration/deceleration movement (i.e., whiplash) without direct external trauma to the head), as manifested by at least one of the following: any loss of consciousness; any loss of memory for events immediately before or after the injury; any alteration in mental status at the time of the incident; or focal neurological deficits that may or may not be transient); (g) inability to tolerate small, enclosed spaces without anxiety (e.g. claustrophobia), as determined by self-report; (h) presence of ferrous-containing metals within the body (e.g., aneurysm clips, shrapnel/retained particles); (i) current or past diagnosis of any bipolar or related disorder or schizophrenia spectrum and other psychotic disorder as determined by the MINI 7.0.2; (j) current severe alcohol or substance use as determined by the MINI 7.0.2; (k) history of pervasive developmental disorder (e.g., Autism, Asperger syndrome). *Exclusion criteria for the PTSD group will be:* (a) current diagnosis of a mood, anxiety, or other disorder that is more clinically salient than PTSD (e.g., MDD, OCD, Panic, GAD); (b) concomitant treatments with medication known to have level 1 evidence for severe drug- drug interactions with dronabinol that are taken daily. *Exclusion criteria for the TEC group will be:* (a) current diagnosis of any obsessive-compulsive and related disorders or trauma- and stressor-related disorders as determined by the MINI 7.0.2 for DSM-5; (b) current diagnosis of any depressive disorder as determined by the MINI 7.0.2 and a score > 22 (indicating very severe depression) on the Hamilton Depression Scale (HAM-D); (c) current diagnosis of any anxiety disorder as determined by the MINI 7.0.2 and a score > 24 (indicating moderate to severe anxiety) on the Hamilton Anxiety Scale (HAM-A).

Termination Criteria

Participants may be terminated for any of the following: (a) participant request to exit or withdraw consent; (b) development of risk of harm to self or others that requires immediate intervention; (c) alcohol, drug, medication use that would interfere with dronabinol or has level 1 evidence for severe drug-drug interaction with dronabinol; (d) development of a systemic, medical, neurologic, or psychiatric illness requiring treatment that would exclude participation; (e) clinical deterioration (see below); (f) non-compliance with study protocol requirements. We will make every effort to ensure that the sessions are accessible (i.e., scheduling sessions during evening and weekend hours). We will attempt to schedule Visits 2-4 on consecutive days, but in the event that this is not possible we will allow no more than 1 week between Visits 2 & 3 and Visits 3 & 4 and no more than 3 weeks between Visits 4 & 5. Of note, if there is more than 1 week between Visit 2 & 3, we will re-do Visit 2 and proceed with the rest of the visits as normal. But once a participant completes Visit 3, Visits 4 & 5 need to be completed within the above timeframe otherwise participation will be terminated. We will make every effort to ensure that appointments are accessible (i.e., scheduling an appointment during evening and weekend hours).

Medical and Neurological Health Determination

All health information collected in the pre-screening and baseline interview (Visit 1) will be reviewed by the PI or Co-I [name], who will indicate whether the participant is medically and neurologically healthy enough to continue in the study. These determinations may be made in person, over the phone, or via e-mail, and will be documented using a Medical Review form.

Emergent Suicidal or Homicidal Risk

The clinician or research staff may remove a participant from the clinical trial if the PI thinks that the participant is at imminent suicidal or homicidal risk. The presence of suicidal ideation is evaluated at the initial assessment. Endorsement of suicidal or homicidal ideation will be addressed in session. If the patient is deemed to have specific suicidal or homicidal ideation, the PI, Co-I [name], or Co-I [name] will be immediately notified and the participant will meet with the PI and/or Co-Is [name] and/or [name], or other licensed social worker/psychologist/psychiatrist covering for the PI or Co-Is on the premises, and the police will be alerted.

Vulnerable Populations

This study will include women of child-bearing potential and college students. However, we will conduct urine pregnancy tests at the screening visit (Visit 1) and at the beginning of Visit 3 to make sure that women are not pregnant. Of note, if the participant is unable to provide a urine sample at Visit 1 (e.g., currently menstruating), we will conduct a urine pregnancy test at the beginning of visit 2. We will also conduct pregnancy tests if the study staff and/or participant have reason to believe they may be pregnant. In addition, participation of college students in this study is completely voluntary, as it is for all participants, and will not be required by any course.

Study Group Assignment

Individuals with PTSD will be randomized to a THC or PBO condition. In our previous studies we have shown that 7.5mg of THC facilitates extinction recall and modulates prefrontal and hippocampal activation in healthy humans volunteers^{55,113}. Moreover, PI [name] has preliminary data to suggest that 7.5mg of THC may facilitate extinction recall in PTSD, but it is not known whether this is the MED. This is an initial step in translation to be tested in the R61 phase. Therefore, we will have a low 5mg condition and a high 10mg condition should 5mg be too low to detect effects. Of note, a 10mg dose of THC does not typically produce anxiety¹⁵¹ or strong negative effects on cognition¹⁵². We aim to identify the MED that facilitates recall of extinction learning. Dronabinol is administered only by the oral route and will be placed in opaque capsules with dextrose filler. Placebo capsules will be identical in appearance but will contain only dextrose. All capsules will be administered to participants in double-blind conditions and participants assigned to receive dronabinol (two-thirds of the PTSD participants) will only receive dronabinol on one occasion.

Study medication, dronabinol or PBO, will be dispensed to participants by PI [name], who possesses a Schedule II-V controlled substance research license through the State of Michigan and the DEA and has experience in the use of dronabinol and PBO in human participant research. A registered pharmacist will handle

the overencapsulation of the required dronabinol and creation of the matching placebo. [name] will store the capsules in her office, [name], in a locked refrigerated safe. She holds current controlled substance licenses from the State of Michigan and Drug Enforcement Administration allowing her to order, store, and dispense dronabinol from her office.

[name] will randomize participants to the study groups: 5 mg dronabinol, 10 mg dronabinol, or placebo. She will dispense one pill from the appropriate container labeled by the pharmacist and put the pill into a separate pill bottle. This new pill bottle will be labeled with the participant specific ID. [name] will be responsible for appropriate documentation of drug orders, inventory, subject-specific drug order forms, dispensing, and disposal records. Research staff associated with the study will give the drug or PBO to participants, and Co-I [name]., a board-certified and licensed physician, or Co-I [name]., a board-certified and licensed psychiatrist, or their physician designate, will be present on-site and/or available by pager/phone.

b. Sources of Materials

Primary Diagnostic Assessments (Table 1)

(1) Mini International Neuropsychiatric Interview Version 6.0.0 (MINI): The MINI is a structured interview for general diagnostic assessment providing an assessment of major psychiatric diagnoses; (2) Clinician-Administered PTSD Scale for DSM-5 (CAPS-5)¹⁵⁴, a validated, gold-standard clinician interview measure of PTSD severity. WSU clinical research staff members will conduct diagnostic interviews using MINI/CAPS instruments. While most interviews will be conducted by one rater, inter-rater reliability will be examined to ensure good reliability (Kappa at least 0.6)¹⁵⁵.

Table 1: R61 Assessment Schedule

	Screening, Informed Consent, & Study Entry	Fear Acquisition	fMRI			
			THC or PBO	Fear Extinction	Extinction Recall Test 1	Extinction Recall Test 2
MINI	✓					
CAPS-5	✓					
Standard Health Questionnaire	✓					
Ethnicity/Race Form	✓					
MRI Safety Form	✓					
Gender Identity Questionnaire	✓					
Concomitant Medication Form	✓					
Handedness Questionnaire	✓					
Connor-Davidson Resilience Scale	✓					
Posttraumatic Growth Inventory	✓					
LEC-5	✓					
PCL-5	✓					
PSQI	✓					
STAI**	✓			✓		
HAM-D	✓					
HAM-A	✓					
BDI-II	✓					
C-SSRS	✓					
WHODAS 2.0	✓					
CTQ	✓					
ERQ	✓					
ACQ	✓					
US Expectancy		✓	✓	✓	✓	✓
SUDS		✓	✓	✓	✓	✓
VAS**			✓			
DEQ**			✓	✓	✓	

ARCI**			✓	
ESQ**			✓	
Blood Draw Safety Questionnaire**			✓	
Debriefing Interview				✓

***These measures are NOT completed by the TEC group at Visit 3, as they do not ingest THC/PBO*

Secondary Measures (Table 1)

(1) Standard Health Questionnaire; (2) Ethnicity/Racial Category Form; (3) MRI Safety Form; (4) Gender Identity

Questionnaire; (5) Concomitant Medication Form. This form will be reviewed and updated (if applicable) by the participant at each study visit; (6) Handedness Questionnaire; (7) Connor-Davidson Resilience Scale (CD-RISC); (8) Posttraumatic Growth Inventory (PTGI); (9) Life Events Checklist for DSM-5 (LEC-5)¹⁵⁶: The LEC-5 is a self-report measure designed to screen for potentially traumatic events in a person's lifetime; (10) PTSD Checklist for DSM-5 (PCL-5)¹⁵⁷: The PCL-5 is a 20-item self-report measure that assesses the 20 DSM-5 symptoms of PTSD. It is used for monitoring symptom change during and after treatment, screening individuals with PTSD, and for making a provisional PTSD diagnosis; (11) Pittsburgh Sleep Quality Index (PSQI)¹⁵⁸: The PSQI is a self-rated questionnaire which assess sleep quality and disturbances over a 1-month time interval; (12) Spielberger State-Trait Anxiety Inventory (STAI)¹⁵⁹: The STAI is a measure of trait and state anxiety; (13) Hamilton Depression Scale (HAM-D)¹⁶⁰: The HAM-D is used to determine a patient's level of depression before, during, and after treatment; (14) Hamilton Anxiety Scale (HAM-A)¹⁶¹: The HAM-A is a questionnaire used by clinicians to rate the severity of a patient's anxiety; (15) Beck Depression Inventory (BDI-II)¹⁶²⁻¹⁶⁵: The BDI-II is self-report questionnaire used to measure severity of depression; (16) Columbia-Suicide Severity Rating Scale (C-SSRS)¹⁶⁶ is a standardized 8 point clinician-administered suicidal rating system designed to track suicidal adverse events across a treatment trial and covering the wide spectrum of suicidality; (17) World Health Organization Disability Assessment Schedule 2.0 (WHODAS 2.0)¹⁶⁷: This is an assessment of global functioning and impairment; (18) Childhood Trauma Questionnaire (CTQ)^{168,169}: The CTQ is a 28-item self-report measure that provides brief, reliable, and valid screening for histories of abuse and neglect. It inquires about five types of maltreatment—emotional, physical and sexual abuse and emotional and physical neglect. (19) Emotion Regulation Questionnaire (ERQ)¹⁷⁰: The ERQ is designed to assess individual differences in the habitual use of two emotion regulation strategies: cognitive reappraisal and expressive suppression; (20) Attentional Control Questionnaire (ACQ)¹⁷¹: The ACQ is a self-report questionnaire designed to measure individual differences to major components of attention: attention focusing and attention shifting. The ability to regulate emotions and focus on the task at hand (e.g., attend to fear-cues) is expected to factor into PE therapy; therefore, the ERQ and ACQ are for exploratory purposes.
